1.2 PILOT DATA

To prepare for BeneFIT, we conducted an observational pilot study²² of children hospitalized for bronchiolitis during the winter of 2016-17. All five BeneFIT medical centers (listed in section 3) participated. Among 199 enrolled subjects, a routine follow-up visit was either recommended or scheduled by the primary team in 84% of cases. Two-thirds of patients who completed the study attended a routine follow-up visit, including 87% of those who had a follow up appointment scheduled prior to hospital discharge and 33% of those for whom as needed follow up was recommended.

"Reassurance provided" (70%) and "education provided" (15%) were cited by parents as the most useful aspect of the follow-up visit. Hospital re-visits were uncommon (2%).

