2.2 SECONDARY OBJECTIVES AND ENDPOINTS

Secondary objectives of the study include determining whether as needed PCP follow-up, compared to scheduled PCP follow-up:

- Does not adversely impact satisfaction with care?
- Does not adversely impact the relationship between the child's primary caregiver and the child's PCP?
- Does not prolong time to resolution of symptoms?
- Does not increase risk of hospital re-admissions and emergency department visits?
- Results in a fewer number of post-discharge ambulatory visits?
- Results in less ambulatory testing (pulse oximetry, chest x-ray) and fewer prescriptions (albuterol, antibiotics, steroids)?
- Results in fewer missed days from daycare and work?
- Results in lower medical costs?

Secondary Outcomes

Measured by parent report via weekly research coordinator phone calls, until symptoms resolved or 50 days after discharge, whichever occurs first:

- Time from hospital discharge to cough resolution
- Time from hospital discharge to child reported back to normal

Measured by parent report via weekly research coordinator phone calls, until symptoms resolved or 50 days after discharge, whichever occurs first:

- Number of hospital re-admissions and emergency visits
- Number of ambulatory visits
- Number of missed daycare and work days
- Ambulatory prescriptions (albuterol, antibiotics, steroids)
- Ambulatory testing (i.e. pulse oximetry, chest x-ray)- only measured at first ambulatory visit

Measured by parent report via research coordinator phone call at 1 month from discharge:

- Relationship with PCP measured by the Patient-Doctor Depth-of-Relationship Scale²⁴
- Satisfaction with care, measured by applicable questions from the Patient Satisfaction Questionnaire Short Form (PSQ-18)²⁵
- Immunizations received

Measured among patients cared for at Intermountain clinics and those who have Select Health insurance:

- Total charges for ambulatory medical care from discharge until:
 - 14 days after discharge
 - symptom resolution

Measured at the time of discharge and during the first follow up phone call:

• Perceptions about pulse oximetry monitoring

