7.2 STATISTICAL ANALYSES

7.2.1 ANALYSIS OF THE PRIMARY AND SECONDARY ENDPOINT(S)

Intent-to-treat analysis for primary outcome

The primary non-inferiority analysis will be an analysis of covariance comparing HADS scores approximately 7 days after discharge between patients randomized to scheduled PCP follow up or as needed PCP follow up, controlling for baseline HADS scores. A 1-sided upper 97.5% confidence bound for the difference in mean HADS score between the intervention and control groups will be constructed, and non-inferiority will be inferred if the upper confidence limit excludes the intent-to-treat non-inferiority (ITT) bound of 1.08 points.

ITT comparisons for secondary outcomes

A log-rank test will be used to compare the time from discharge to the first report of symptom resolution between the randomized treatment groups. Follow-up for symptom resolution will be right-censored at 50 days after discharge or at the time of loss-to-follow-up. Charges will be compared between the two intervention groups using two-part models, given that charge data will likely be semi-continuous. Other secondary outcomes will be compared between the randomized groups using Poisson or negative binomial models with robust standard errors for statistical inference.

Instrumental variable analysis of the effect of the routine follow-up visit

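### The secondary objective concerns medical costs, but its only outcome is ambulatory charges, which cannot show whether medical costs are lower

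*Combined protocol and SAP*

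**What the plan says.** Section 2.2 lists among the secondary questions whether as needed follow-up "Results in lower medical costs". The one outcome expressed in money is "Total charges for ambulatory medical care from discharge until" each of two end points: 14 days after discharge, and symptom resolution. It is "Measured among patients cared for at Intermountain clinics and those who have Select Health insurance".

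Hospital use appears in the same section as "Number of hospital re-admissions and emergency visits", on a separate line from "Number of ambulatory visits". It is counted and not costed.

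Section 7.2.1, under the ITT comparisons for secondary outcomes, says: "Charges will be compared between the two intervention groups using two-part models, given that charge data will likely be semi-continuous". It adds no emergency or inpatient component and does not say when membership of the charge subset is judged. Its only censoring rule (50 days or loss to follow-up) is given for the log-rank test of symptom resolution, not for charges.

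Section 1.2 reports routine-visit attendance in the pilot of "87% of those who had a follow up appointment scheduled prior to hospital discharge" and 33% of those advised to return as needed, with hospital re-visits in 2%. Section 7.1 reuses the same attendance figures as its non-adherence assumptions (13% and 33%).

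**The concern.** The question is broader than the measurement. The arms differ by an instruction about one ambulatory visit, so ambulatory charges are expected to fall with as needed follow-up because that visit happens less often. In that respect the outcome largely repeats another secondary question, whether there are fewer ambulatory visits.

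Cost is also part of the study's stated rationale in section 1.1, so a result on this outcome is likely to be read as an answer about medical costs. If hospital use differs between the arms, in either direction, the cost comparison as planned will not register it.

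The second window adds a smaller difficulty. It closes at symptom resolution, which is itself a secondary outcome that may differ by arm. Charges would then accumulate over periods whose length can depend on assignment.

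**Working it through.** **The plan's own figure.** The only sample size in the documents is for the primary HADS analysis. With SD 4.1, correlation 0.65, margin 1.08, one-sided alpha 0.025 and 80% power, the residual SD is 4.1 × √(1 − 0.65²) = 3.116. Then n = 2 × (1.960 + 0.842)² × 3.116² / 1.08² = 131 per arm. Dividing by 0.90 for follow-up gives 146 per arm, or 292, against the stated 294. It reproduces within two patients. No size or power is stated for charges.

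**Inputs for the cost question.** Attendance of 87% and 33% and a re-visit rate of 2% come from section 1.2; 147 per arm comes from section 7.1. The ratio k of the charge for one hospital event to the charge for one ambulatory visit is not in the documents. It is an assumption, taken here from 10 to 100.

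**Step 1: expected ambulatory difference.** 0.87 − 0.33 = 0.54 routine visits per child, or 0.54 × 147 ≈ 79 visits per arm. This treats other ambulatory use as equal between arms.

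**Step 2: break-even.** The saving is cancelled when the extra hospital events per child reach 0.54 / k. Power in the third column is for detecting 2% against 2% plus the break-even rise, from Φ(d / √[(p₁q₁ + p₂q₂)/n] − 1.96) with n = 147, two-sided 5%.

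| k (assumed) | Break-even rise | Power of the event comparison |
|---|---|---|
| 10 | 5.4 points (about 8 events per 147) | 59% |
| 20 | 2.7 points (about 4) | 25% |
| 50 | 1.1 points (about 1.6) | about 9% |
| 100 | 0.5 points (about 0.8) | lower still |

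For k = 50: 0.011 / √[(0.0196 + 0.0300)/147] − 1.96 = 0.60 − 1.96 = −1.36, so power is 0.087. A doubling from 2% to 4%, which is break-even at k = 27, has 17% power.

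**Step 3: what the separate counts can exclude.** At 2% in both arms, about 0.02 × 147 ≈ 3 children per arm have an event. The 95% half-width for the risk difference is 1.96 × √(0.02 × 0.98) × √(2/147) = 0.032, or 3.2 points. The counts therefore cannot exclude a cancelling rise once k exceeds 0.54 / 0.032 ≈ 17.

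**Step 4: what total charges could show.** Multiplying the same half-width by k gives the imprecision in the total from hospital events alone: 0.32, 0.64, 1.6 and 3.2 visit-equivalents for k = 10, 20, 50 and 100. Above k of about 17 this exceeds the 0.54-visit saving. These figures use 147 per arm; the charge subset is smaller, so its interval would be wider.

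**Step 5: the windows.** Fourteen days is fixed. Symptom resolution is not, and no rule for charges covers children unresolved at 50 days or lost before resolution.

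**The case against.** The best defence is that nothing is hidden. Readmissions and emergency visits are a secondary outcome in their own right, are not limited to the charge subset, and are supplemented by record review (section 6.2). A reader would see them beside the charge result, and one fixed window already exists. This stands as far as it goes: the information is collected. But at about three events per arm the counts cannot show that an ambulatory saving is not offset.

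A second objection is that total charges would depend on those same few events and may fail to show a real saving. Step 4 confirms this. It limits what the added outcome can deliver, but it does not turn ambulatory charges into an answer about medical costs.

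Three stronger readings are tempting and are not supported.

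- A reader might infer that the charge subset excludes as needed families who make no visit, which would be a selection made after randomization. The wording on Intermountain clinics has no time point, but the comparison sits under ITT, the two-part model is chosen because charges are expected to be semi-continuous (so zeros are expected), and insurance is an alternative route of entry. The natural reading is that zero-charge children stay in.
- A reader might infer that the omission favours as needed follow-up. The direction is unknown. Section 1.1 cites a trial in which a post-discharge home visit was associated with more acute reuse; if that applied here, ambulatory charges would understate the saving.
- A reader might infer that ambulatory charges must fall. They are expected to, but section 6.1 tells as needed families to return if the child does not improve or new concerns arise, and those visits carry charges too.

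**Conclusion.** The point holds as a mismatch between a cost objective and an ambulatory-charge outcome. Following the plan as written could lead to a statement about medical costs that the outcome cannot establish. The expected ambulatory difference is about 0.54 visits per child. The rise in hospital events that would offset it ranges from 5.4 points at k = 10 to 0.5 points at k = 100, and the separate counts cannot exclude such a rise once k exceeds about 17.

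These sizes rest on the pilot attendance rates, on equal ambulatory use apart from the routine visit, and on k, which the documents do not give. The pilot's 2% is for hospital re-visits, which are not defined as readmissions and may include emergency visits, so one k for all events is a simplification. Lower charges for tests or prescriptions would raise the break-even.

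The window ending at symptom resolution is a real but lesser weakness. The subset wording needs clarifying and is not shown to cause bias. This is a secondary outcome: the primary analysis and N = 294 are unaffected.

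**What to change.** 1. Limit the conclusion drawn from the existing outcome to ambulatory charges, and word the objective in section 2.2 to match.
2. Where the same billing sources hold them, add total charges (ambulatory, emergency and inpatient) over fixed windows of 14 and 50 days, with ambulatory charges reported as a labelled component.
3. Replace the symptom-resolution window with the fixed 50-day window.
4. In section 7.2.1, report the combined mean difference from the two-part model with a confidence interval, so that both parts contribute to one estimate.
5. As a clarification only, state that subset membership is set at enrolment, by usual PCP clinic or insurer, and that children with zero charges are retained.

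The cost is a wider billing query and a few sentences of SAP text. The interval for total charges will be wide and may not show a saving of the expected size; reporting the ambulatory component alongside keeps the more precise comparison. The documents do not say whether hospital charges are available for every child in the subset. If they are not, item 1 is the minimum change.

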3 STUDY DESIGN

The BeneFIT trial will be a multicenter, unblinded randomized trial. The study will take place within the inpatient units at 2 tertiary children's hospitals (Primary Children's Hospital, Lucille Packard Children's Hospital- Palo Alto, CA) and 3 affiliated community hospitals (Riverton Hospital, UT; John Muir Hospital, CA; Packard El Camino Hospital, CA). Data will also be collected via phone calls from the research team after patients have been discharged from the hospital.

3.1 END OF STUDY DEFINITION

The participant is considered to have completed the study after the final follow-up phone call has been conducted or at the time they withdraw from continued study participation.

4 STUDY POPULATION

4.1 INCLUSION CRITERIA

Children less than two years of age who are hospitalized with an attending physician diagnosis of bronchiolitis will be considered for enrollment.

4.2 EXCLUSION CRITERIA

- Chronic lung disease (any baseline supplemental oxygen need or on diuretics, including CF or other bronchiectasis)
- Complex or hemodynamically significant heart disease (planned surgery, medications)
- Immunodeficiency
- Neuromuscular disease
- Discharged home with medication for withdrawal (narcotic or benzodiazepine)
- Inpatient team believes the child should follow up with their PCP
- Patient enrolled during previous hospitalization (does not need to be re-enrolled)

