2 OBJECTIVES AND ENDPOINTS

2.1 PRIMARY OBJECTIVE AND ENDPOINT

The primary objective of the study is to determine whether as needed Primary Care Physician (PCP) follow-up is non-inferior to scheduled PCP follow-up in terms of reduction in parental anxiety.

Primary Outcome

Parental anxiety, as measured by the anxiety portion of the Hospital Anxiety and Depression Scale (HADS),²³ a validated tool used in a previous trial among parents whose children had been hospitalized for bronchiolitis.¹⁹ Parental anxiety will be measured by research coordinators at before hospital discharge (baseline) and at the first data collection phone call (5-9 days following discharge). The same parent will be interviewed for both the baseline and the follow up HADS. If the length of time between baseline HADS and actual discharge exceeds 2 days, the HADS will be repeated, such that each subject has a baseline HADS within 2 days of hospital discharge.

Justification of Primary Outcome

Our primary outcome was selected based on feedback from primary care providers and parents of children hospitalized for bronchiolitis. Among parents surveyed in our pilot study, "reassurance" was most commonly selected (70%) as the most valuable aspect of the follow up visit.²² Parental reassurance was also mentioned repeatedly by primary care providers from Stanford, Intermountain, and elsewhere via informal discussions with the investigators.

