6 STUDY ASSESSMENTS AND PROCEDURES

6.1 STUDY INTERVENTION

Scheduled follow up

At the time of hospital discharge, parents will be instructed to have their child follow up with their PCP within 4 days of discharge regardless of improvement and/or symptom resolution. Research coordinators will verify that the child has a scheduled follow up appointment prior to discharge and will help with scheduling if necessary.

As needed follow up

At the time of hospital discharge, parents will be instructed that the child does not need to automatically follow up with his/her primary care physician. Rather, the child should follow up on an as needed basis: if the child does not improve or if new concerns arise.

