6.3 MEASURES TO MINIMIZE BIAS: RANDOMIZATION AND BLINDING

Randomization

After consent and enrollment, a research coordinator at the site will obtain a site-specific computergenerated randomization assignment for each patient. Patients will be randomized with equal (1:1) allocation to either the scheduled PCP follow up group or to the as-needed PCP follow up group, using randomly permuted blocks of random sizes. Randomization sequences will be stratified by site but not by any additional baseline factors. The research coordinator will inform the patient's family, inpatient medical team, and PCP of the patient's assignment.

Blinding

BeneFIT will be an unblinded trial because it will not be feasible to blind parents or research coordinators to intervention assignment, as the reason for any follow-up visit (i.e. routine vs new concern) that occurs needs to be documented. However, investigators responsible for analyses will be blinded to individual patient intervention assignments.

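### Section 4.2 bars re-enrolling the same child but not a sibling, so one parent can be placed in both arms of a trial whose outcome is that parent's anxiety

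*Combined protocol and SAP*

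**What the plan says.** Eligibility is defined on the child. Section 4.1 states: "Children less than two years of age who are hospitalized with an attending physician diagnosis of bronchiolitis will be considered for enrollment". Section 4.2 limits repeat enrollment only through "Patient enrolled during previous hospitalization (does not need to be re-enrolled". Neither section, nor any other part of the document, mentions twins, siblings or one child per family.

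Section 6.3 provides a "computergenerated randomization assignment for each patient", at a 1:1 ratio, and adds: "Randomization sequences will be stratified by site but not by any additional baseline factors". Nothing ties the assignments of two children from one family together.

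The intervention in section 6.1 is addressed to the parent. In one arm "parents will be instructed to have their child follow up with their PCP within 4 days of discharge"; in the other "parents will be instructed that the child does not need to automatically follow up".

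The primary outcome in section 2.1 is the parent's HADS anxiety score, taken before discharge and 5-9 days after it. That section also says: "The same parent will be interviewed for both the baseline and the follow up HADS". Section 7.2.1 analyzes the score by ANCOVA on baseline HADS and says nothing about two records from one parent. Section 7.1 makes no allowance for shared parents in its total of 294.

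**The concern.** The unit randomized is the child, while the unit that receives the instruction and supplies the outcome is the parent. For most families these coincide. For co-admitted siblings they do not.

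When two such children are assigned to different arms, three things follow:

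- One parent is given both instructions.
- A visit made for the scheduled child can reassure the same parent in respect of the as-needed child, so the contrast under test is lost for that parent.
- If that parent answers for both children, nearly the same HADS score is counted once in each arm and contributes almost no difference.

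In a superiority trial, shrinkage toward zero would be conservative. Here non-inferiority is declared when the upper confidence limit lies below 1.08 points, so shrinkage makes that conclusion easier to reach when as needed follow-up is in fact worse.

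**Working it through.** **Inputs from the documents.** Section 7.1: SD 4.1, baseline-to-7-day correlation 0.65, ITT margin 1.08, one-sided alpha 0.025, power 80%, true difference 0, 90% follow-up, total 294. Section 6.3: 1:1 allocation in permuted blocks of random, unstated size.

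**Assumption, not in the documents.** A share f of children belong to pairs that share one parent score. I take f = 2-5%, with 10% as an extreme.

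**1. The plan's sample size reproduces.**
- Residual SD = 4.1 × √(1 − 0.65²) = 3.116.
- Normal approximation: 2 × [3.116 × (1.960 + 0.842) / 1.08]² = 130.7, so 131 evaluable per arm. Then 131/0.9 gives 146 per arm, 292 in total.
- With the t distribution, 132 evaluable per arm are needed. Then 132/0.9 = 146.7, so 147 per arm and 294 in total, as stated.
- Standard error of the difference = 3.116 × √(2/132) = 0.384.

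**2. Number of pairs.** 0.02 × 294 to 0.05 × 294 is about 6-15 children, or 3-7 pairs. If half the pairs are discordant, about 3-7.5 children (1.0-2.5% of 294) have a parent score that appears in both arms.

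**3. Dilution.** A discordant pair with one shared score adds zero to the arm difference. With d the share of pairs that are discordant, expected estimate = true difference × (1 − f × d).
- f = 2%, d = 0.5: 1.08 becomes 1.069.
- f = 4%, d = 0.5: 1.08 becomes 1.058.
- f = 5%, d = 0.5: 1.08 becomes 1.053.

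Two assignments within one block of size b differ with probability (b/2)/(b − 1), which exceeds one half, so d = 0.5 is a low value for siblings randomized back to back. The limit is d = 1, where dilution equals f, that is 2-5%.

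**4. Standard error.** Relative to independent records, the variance of the difference is multiplied by about 1 − f × (2d − 1). Concordant pairs raise it and discordant pairs lower it. At d = 0.5 the factor is 1. Above 0.5 it is below 1, so the ANCOVA standard error is slightly too large. A simulation of the ANCOVA agrees: with 2-10% of children in pairs, the mean model standard error was 0.384 and the empirical one 0.384-0.387.

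**5. Type I error at a true difference of 1.08, d = 0.5.** The estimate shifts by 1.08 × f/2, so the error is Φ(−1.96 + 1.08 × f/2 / 0.384).
- f = 2%: Φ(−1.932) = 2.7%.
- f = 5%: Φ(−1.890) = 2.9%.

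A simulation (20,000 runs per setting, 264 evaluable children, independent 1:1 assignment within pairs, Monte Carlo error about 0.1 point) gave 2.4% with no pairs and 2.6%, 3.0%, 3.0% and 3.3% at f = 2%, 4%, 6% and 10%.

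**6. Power at a true difference of 0.** Dilution of zero is zero. Simulated power was 79.7-80.0% for f = 2-10%, against 80.2% with no pairs.

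**The case against.** The strongest reply is that this is negligible and rests on an assumed rate. The plan already cuts its margin from 2 to 1.08 for an expected 33% + 13% = 46% of patients whose visit attendance departs from assignment. Another 1-2.5% of dilution is minor beside that, and at the planning assumption of no difference it has no effect. All of this stands, and it sets the weight of the point.

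Three stronger readings are tempting, and the documents do not support them.

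- **That concordant pairs make the confidence bound too narrow, so two errors favor non-inferiority.** Concordant pairs alone would do so, but discordant pairs act the other way. Under 1:1 assignment the two roughly cancel, and permuted blocks tip the balance toward a standard error that is too large. Only dilution remains.
- **That any two siblings put the same score in both arms.** Section 2.1 times HADS to each child's own discharge. A sibling admitted later brings a new baseline and a new follow-up, which are correlated with the first pair but not identical. The same-parent rule joins the two time points for one child. It does not say who answers when two siblings are enrolled.
- **That parent-level secondary outcomes are biased in the same favorable direction.** Section 2.2 asks whether as needed follow-up leads to fewer missed work days. Dilution there works against showing that benefit.

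**Conclusion.** The gap is real and confined to siblings. Its clearest form is co-admitted siblings, such as twins, assigned to different arms with the same parent interviewed for both. What remains is direct contamination of that parent plus a small anti-conservative dilution. The dilution is about 1-2.5% if 2-5% of children are in such pairs and half the pairs are discordant, and somewhat more under permuted blocks. One-sided type I error at the 1.08 margin is then about 2.6-3.0% against 2.5%, with power at zero difference unchanged.

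These figures assume identical scores within a pair, which is the worst case, and a sibling rate that the documents do not give. A reader might infer that the sample size or the primary conclusion is unsafe. It is not: 294 reproduces, and the standard error is not understated on net. This is a cheap improvement, not a flaw that threatens the trial.

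**What to change.** Add one exclusion to section 4.2: *Parent or sibling already enrolled in the trial.* Where eligible siblings are in hospital together, choose one index child by a fixed rule before randomization, for example the first entered on the RedCap enrollment checklist. Each parent then receives one instruction and supplies one score, and the total of 294 stands.

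The cost is one line of protocol, one checklist item and a handful of eligible children not enrolled. Randomizing co-enrolled siblings as one unit, with one score per parent in the analysis, would also keep a parent out of both arms without turning children away, but it needs more changes to the randomization and analysis text. Family-clustered standard errors alone would not do, because they leave the dilution from discordant pairs in place.
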